Event - After at most one missing or inadequate post-baseline disease assessment, OR - \leq 24 weeks after the date of randomization	Date of event	Event
Event - After 2 or more missing or inadequate post-baseline disease assessments	Date of last adequate disease assessment [b] documenting no event	Censored
No event	Date of last adequate disease assessment [b] documenting no event	Censored

[a] However, if the participant dies \leq 24 weeks after the date of randomization the death is an event with date on death date

[b] An adequate post-baseline disease assessment is defined as an assessment with progression of disease (all participants), recurrence of high-grade disease (all participants), recurrence of low-grade disease (all participants), CR (participants with CIS at randomization), persistence of CIS disease (participants with CIS at randomization), or no evidence of disease (participants with papillary disease and no CIS at randomization).

Key Secondary Estimand (OS): treatment effect, estimated based on data from all randomized participants, of each experimental arm (Arm A and Arm B) on OS compared to Arm C regardless of tolerability, duration of study treatment, initiation of subsequent anti-cancer therapy or participant's request to discontinue study procedures.

- Variable: OS.

- Censoring: data for participants not known to have died are censored at the time of last contact.
- Population-level summary measure: hazard ratio for OS, including all randomized participants.

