## 2. INTRODUCTION

This SAP provides the detailed methodology for summary and statistical analyses of the data collected in Study B8011006. This document may modify the plans outlined in the protocol; however, any major modifications of the primary endpoint definition or its analysis will also be reflected in a protocol amendment.

A separate SAP will cover the periodic safety review by the External Data Monitoring Committee (E-DMC).

Statistical analyses will be performed using cleaned electronic case report form (eCRF) data as well as non-CRF data (i.e., PRO, pharmacokinetic (PK) concentration, anti-drug antibody (ADA), neutralizing antibody (Nab), biomarker data, and Blinded Independent Central Review (BICR) of pathology, imaging, and oncology review data).

As of 31 August 2022, enrollment in Cohorts B1 and B2 was closed by the sponsor for business strategy reasons. This decision was not made due to any safety concerns, new emerging data, or regulatory interaction. Due to the decision to close enrollment in Cohorts B1 and B2, the Cohort B1 and B2 study objectives are no longer required.

As of 17 June 2024, the Protocol Amendment 5 revised the Cohort A study analysis plan for the primary and key secondary objectives. The rationale for this change is based on the observation from pooled treatment groups that EFS events are accumulating at a much slower rate than originally projected, together with an increasing rate of participants dropping out from EFS observation. The IA2 will be removed, and the FA for EFS based on a calendar-based data cut-off date will be conducted. Randomization to Cohort A was completed on 16 November 2021 and the EFS FA data cut-off date will be set to allow for approximately 3 years of follow-up after the last participant was randomized. The treatment period was completed on 16 November 2023. Based on the blinded observed EFS events accrual rate and assuming equal event rate across three arms, approximately 261 EFS events are expected to have occurred across all three arms (approximately 174 events for each two-arm comparison) by the EFS FA data cut-off date.

Data for Cohorts B1 and B2 will be reported at the time of PCD for Cohort A.

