### **5.2.11. Adequate post-baseline disease assessment**

An adequate post-baseline disease assessment is defined as an assessment recorded with progression of disease (all participants), recurrence of high-grade disease (all participants), recurrence of low-grade disease (participants without CIS at randomization (Cohort A/Cohort B2), CR (participants with CIS at randomization (Cohort A)/baseline (Cohort B1)), persistence of CIS disease (participants with CIS at randomization (Cohort A)/baseline (Cohort B1), or no evidence of disease (participants without CIS at randomization (Cohort A)/baseline (Cohort B2)) (Section 5.2.12). Time points where the response is not evaluable (NE) or no assessment was performed will not be used for determining the censoring date.

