### **5.2.12. Disease Assessments**

Disease will be assessed based on reported results from cytology, cystoscopy, biopsy, and imaging scans at different evaluation time points from the ‘start date’ until the first documentation of progression of disease, recurrence of high-grade disease, or persistence of CIS disease according to the following rules.

**Complete Response**, in participants with CIS at randomization (Cohort A)/baseline (Cohort B1), is defined as:

- histologic disappearance of malignancy on bladder biopsy with negative cytology and cystoscopy; or
- negative cytology and positive cystoscopy with biopsy-proven low-grade Ta lesion or non-malignant tissue.

The date of biopsy, cystoscopy, or cytology (whichever is earliest) will be used as the date of CR.

**Persistence of CIS**, in participants with CIS at randomization in Cohort A, is defined as persistence of CIS after induction or re-induction (if re-induction is administered). For participants in Cohort B1, persistence of CIS is defined as persistence of CIS at the 12-week disease assessment. This will require a cystoscopy or cytology positive result with biopsy positive for CIS. The date of positive biopsy, cystoscopy, or cytology (whichever positive result is earliest) will be used as the date of persistence of CIS.

**Recurrence of high-grade disease** is defined as re-appearance of high-grade disease (high-grade Ta, T1 or CIS) after ‘start date’ for the following 1) participants without CIS at baseline, 2) after CR for participants with CIS at baseline, or 3) before CR for participants with CIS and concurrent papillary disease at baseline in Cohort A or B1. This will require a cystoscopy or cytology positive result, with biopsy positive for T1, high-grade Ta and/or

CIS. The date of positive biopsy, cystoscopy, or cytology (whichever positive result is earliest) will be used as the date of recurrence of high-grade disease. If recurrence of high-grade disease occurs at the time of progression, progression should be the event. For participants with CIS at randomization, appearance of high-grade disease after a CR is considered recurrence of high-grade disease, while appearance of high-grade disease before a CR is progression.

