**Recurrence of low-grade disease** is defined as re-appearance of low-grade disease (low-grade Ta) after ‘start date’. This will require a cystoscopy or cytology positive result, with biopsy positive for low-grade Ta. The date of positive biopsy, cystoscopy, or cytology (whichever positive result is earliest) will be used as the date of recurrence of low-grade disease.

**Progression of disease is defined** as any of the following:

- Lamina propria invasion (e.g., increase from Ta to T1 or CIS to T1)
- Muscle invasive disease (stage  $\geq$  T2)
- Lymph node positive disease (N+)
- Metastatic disease (M1)
- Appearance of high-grade Ta or T1 in participants with CIS only at baseline (Cohort A and Cohort B1) before achieving a CR.

This will require a cystoscopy or cytology positive result with imaging positive and/or biopsy positive for disease progression as described above. The date of positive biopsy, imaging for new lesion, positive cystoscopy, or positive cytology (whichever result is earliest) will be used as the date of progression.

**No Evidence of Disease:** only applies to participants without CIS at baseline (Cohort A and Cohort B2) and is defined as disease that was completely resected prior to ‘start date’ and does not meet the criteria of progression of disease, recurrence of high-grade disease, or recurrence of low-grade disease while on study.

The date of imaging, biopsy, cystoscopy, or cytology (whichever result of the available assessments is earliest) that supports no evidence of disease will be used as the date of no evidence of disease.

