**Table 10. Possible Clinical Outcomes for Participants With or Without CIS at Randomization and EFS Evaluation**

Population	Disease Assessment	EFS Event Y/N
Participants with CIS at randomization	Progressive disease [a] before achieving a CR for participants with CIS only at randomization	Y
	Progressive disease after achieving a CR	Y
	Recurrence of high-grade disease before achieving a CR for participants with CS and concurrent papillary disease at randomization	Y
	Recurrence of high-grade disease after achieving a CR	Y
	Persistence of CIS (non-CR) [b]	Y
	Recurrence of low-grade disease	N
Participants without CIS at randomization	Progressive disease	Y
	Recurrence of high-grade disease	Y
	Recurrence of low-grade disease	N

[a] Including appearance of new high-grade Ta or T1 disease for participants with CIS only at randomization.

[b] Persistence of CIS after induction, with CR after re-induction is not considered an event.

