**Table 11. Outcome and Event Dates for the Primary Analysis of EFS-Cohort A**

Scenario	Date of event/censoring	Outcome
No adequate baseline assessment	Date of randomization [a]	Censored [a]
Event - After at most one missing or inadequate post-baseline disease assessment, OR - $\leq 24$ weeks after the date of randomization	Date of event	Event
Event - After 2 or more missing or inadequate post-baseline disease assessments	Date of last adequate disease assessment documenting no event	Censored
No event	Date of last adequate disease assessment documenting no event	Censored

[a] However, if the participant dies  $\leq 24$  weeks after the date of randomization the death is an event with date on death date

The primary efficacy analysis will compare the EFS time based on the investigator assessment between Arm A and Arm C and will be performed using a 1-sided stratified log-rank test as described in [Section 5.1](#). The following analyses will be based on the FAS.

The treatment effect will be estimated using a Cox's Proportional Hazard model stratified by the randomization strata to calculate the hazard ratio along with 95% CIs. Each stratum will define a separate baseline hazard function (using the 'STRATA' statement in SAS PROC PHREG), ie for the i-th stratum the hazard function is expressed as:  $h(i;t) = h(i,0;t) \exp(x\beta)$ ,

where  $h(i,0;t)$  defines the baseline hazard function for the  $i$ -th stratum and  $x$  defines the treatment arm (0=control arm, 1= experimental arm) and  $\beta$  is the unknown regression parameter.

Ties will be handled using the Exact option in SAS (Ties=Exact option in SAS PROC PHREG).

Kaplan-Meier estimates (product-limit estimates) will be presented by treatment arm together with a summary of associated statistics including the median EFS time with 2-sided 95% CIs. In particular, the EFS rate at 6, 12, 18, 24, 30, 36, 42, and 48 months will be estimated with corresponding 2-sided 95% CIs. The CIs for the median will be calculated according to Brookmeyer and Crowley (1982) and the CIs for the survival function estimates at the time points defined above will be derived using the log-log transformation according to Kalbfleisch and Prentice (2002) (conftype=loglog default option in SAS Proc LIFETEST) with back transformation to a CI on the untransformed scale. The estimate of the standard error will be computed using Greenwood's formula. A Kaplan-Meier plot for EFS will be generated.

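### Protocol and SAP disagree on whether low-grade recurrence is an adequate assessment in CIS participants, so a few high-grade EFS events could count under one document and be censored under the other (minor)

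*SAP*

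**What the plan says.** The two documents define an adequate post-baseline assessment differently.

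- Protocol 9.1.1.1, Table 3, footnote [b], includes "recurrence of low-grade disease (all participants), CR (participants with CIS at randomization", so low-grade recurrence is adequate whether or not the participant had CIS.
- SAP 5.2.11 includes "recurrence of low-grade disease (participants without CIS at randomization (Cohort A/Cohort B2", so CIS participants are left out.

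The censoring rule that uses the definition is the same in both (Protocol Table 3, SAP Table 11). An event found "After 2 or more missing or inadequate post-baseline disease assessments" is censored at the last adequate assessment, unless it falls within 24 weeks of randomization.

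Elsewhere the SAP does not follow its own restriction. Section 5.2.12 says low-grade recurrence "is defined as re-appearance of low-grade disease (low-grade Ta) after" the start date, with no limit to participants without CIS. Table 10 lists "Recurrence of low-grade disease" as a non-event outcome for participants with CIS. Time to low-grade recurrence (SAP 6.2.2.8) is analysed in the full analysis set, which includes them.

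The CR definition covers part of the gap. In a CIS participant, "negative cytology and positive cystoscopy with biopsy-proven low-grade Ta lesion or non-malignant tissue" is CR, and CR is adequate in both documents. Low-grade recurrence carries no cytology condition of that kind: "This will require a cystoscopy or cytology positive result, with biopsy positive for low-grade Ta".

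SAP 2.1, which lists departures from the protocol, names only CR and duration of CR by BICR.

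**The concern.** Adequacy decides whether an observed EFS event is counted or removed, and where a participant without an event is censored. Two current documents that differ on it can give different event counts and censoring dates for the primary endpoint from the same data. The same definition feeds the censoring reasons in SAP Table 12 and the duration-of-CR rule in SAP Table 17, where the whole population had CIS at randomization. The trial is already short of EFS events (SAP 2), so a rule that discards observed ones should be a stated choice rather than a by-product of inconsistent wording.

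**Working it through.** **1. The plan's power figure.** SAP 5.1.1 gives 174 events, HR 0.69 and one-sided alpha 0.025. Power = Φ(|ln 0.69| × √(d/4) − 1.96).

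- d = 174: 0.371 × 6.596 − 1.96 = 0.487, power 68.7%, as stated.
- d = 173: 68.45%. d = 172: 68.2%.

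Each event lost from a two-arm comparison costs about 0.25 points.

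**2. The two definitions applied to the same histories.** All are CIS participants in CR at weeks 12 and 24. HG is high-grade recurrence, LG is biopsy-proven low-grade Ta.

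| History after week 24 | Protocol | SAP |
|---|---|---|
| (a) LG with negative cytology at 36 and 48, HG at 60 | event, week 60 | event, week 60 |
| (b) CR at 36, LG with positive cytology at 48, HG at 60 | event, week 60 | event, week 60 |
| (c) LG with positive cytology at 36 and 48, HG at 60 | event, week 60 | censored, week 24 |
| (d) LG with positive cytology at 36, week 48 missed, HG at 60 | event, week 60 | censored, week 24 |
| (e) LG with positive cytology at 36, no event, last visit | censored, week 36 | censored, week 24 |

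In (a) both visits are CR, so the documents agree. In (b) one inadequate visit is not enough to trigger censoring. They part only in (c), (d) and (e).

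**3. How many events.** The documents give no frequency for such visits, so these inputs are assumptions:

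- 264 CIS participants: the planned minimum is 250 of about 999 (25%), and 0.25 × 1056 randomized = 264;
- a 3.5% chance of high-grade recurrence per 12-week visit after week 24;
- 7% of visits missed;
- 1% to 3% of visits recorded as low-grade and not CR;
- visits every 12 weeks from week 36 to 96, then at 120 and 144;
- the two missing or inadequate assessments are consecutive and come directly before the event.

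Simulated extra events censored under the SAP, trial-wide: about 0.1 to 0.3 if the low-grade status lasts one visit, and about 0.6 to 2.2 if it lasts two.

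**4. Conversion to power.** A two-arm comparison holds two of the three arms.

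- Upper end: 2.2 × 2/3 ≈ 1.5 events. At d = 172.5, power is 68.3%, a loss of about 0.4 points.
- Lower end: 0.1 × 2/3 ≈ 0.07 events, a loss of about 0.07 × 0.25 ≈ 0.02 points.

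**The case against.** The restriction looks deliberate. The SAP version 3 entry in the change log records adding it, and it fits a CR definition that already absorbs low-grade Ta with negative cytology. What remains is mostly low-grade Ta with positive or indeterminate cytology. Protocol 8.1.1.2 counts cytology suspicious for high-grade carcinoma as positive, and an unsatisfactory sample as indeterminate. Declining to accept such a visit as showing no event in a CIS participant is defensible. This stands: a reader might infer that these visits were fully assessed as event-free and that censoring has no rationale, but the documents do not support that.

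The plan also has a safeguard. SAP 6.2.2.3 prespecifies an EFS analysis that counts every event regardless of missing or inadequate assessments, and Table 12 tabulates this censoring reason by arm. Lost events would therefore show. The safeguard is partial. It also restores events after visits that were truly missed, so it cannot isolate this discrepancy. It leaves the earlier censoring in history (e) untouched, does not cover duration of CR, and does not say which primary rule governs.

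A reader might also see a breach of the SAP's undertaking that "any major modifications of the primary endpoint definition or its analysis will also be reflected in a protocol amendment". SAP 2 says just before this that the SAP may modify the protocol's plans, and a change of this size is hard to call major. The point does not rest on that sentence.

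Intent in an earlier SAP version does not settle the matter. The SAP is based on Protocol Amendment 5, which is later than that change and still accepts low-grade recurrence in all participants.

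**Conclusion.** The inconsistency is real, current and located in the primary endpoint's censoring rule. Its reach is narrow. It needs a CIS participant, a low-grade finding not classed as CR, at least one further inadequate or missed visit, and an event more than 24 weeks after randomization. For participants without an event, it needs such a finding at the last visit. Under the assumed rates the effect is about 0.1 to 2 EFS events trial-wide and at most about 0.4 points of power. Severity is minor.

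Three stronger readings are not supported:

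- That every low-grade finding in a CIS participant becomes inadequate. Those with negative cytology meet the CR definition.
- That the treatment comparison is biased. CIS participants with such findings may be at higher risk, but nothing in the documents shows a difference between arms.
- That the two inadequate assessments may be counted cumulatively over follow-up. Table 11 does not say consecutive, and on the same assumptions a cumulative count would give about 0.6 to 6.5 events. But it would also censor events that directly follow an adequate visit, which serves no purpose in a rule for assessment gaps.

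The size depends on how sites record low-grade Ta with positive or indeterminate cytology. That may be governed by the decision diagram in Protocol 10.9, which I could not see.

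**What to change.** Before arm-level data are summarised, use one definition in both documents.

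- **Default:** in SAP 5.2.11, return low-grade recurrence to the protocol's scope of all participants, and apply it to Tables 11, 12 and 17. An observed EFS event is then not removed because preceding visits were recorded as low-grade recurrence. Table 20 needs no change, because low-grade recurrence is itself the event there and only its first documentation counts.
- **If the restriction is kept:** align Protocol Table 3, SAP 5.2.12 and SAP Table 10 with it, state how a low-grade finding that is not CR is classed in CIS participants, and list the change in SAP 2.1.

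The default costs one phrase and one programming condition. The alternative also needs the protocol footnote amended. Neither needs new data.

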### **5.2.12. Disease Assessments**

Disease will be assessed based on reported results from cytology, cystoscopy, biopsy, and imaging scans at different evaluation time points from the ‘start date’ until the first documentation of progression of disease, recurrence of high-grade disease, or persistence of CIS disease according to the following rules.

**Complete Response**, in participants with CIS at randomization (Cohort A)/baseline (Cohort B1), is defined as:

- histologic disappearance of malignancy on bladder biopsy with negative cytology and cystoscopy; or
- negative cytology and positive cystoscopy with biopsy-proven low-grade Ta lesion or non-malignant tissue.

The date of biopsy, cystoscopy, or cytology (whichever is earliest) will be used as the date of CR.

**Persistence of CIS**, in participants with CIS at randomization in Cohort A, is defined as persistence of CIS after induction or re-induction (if re-induction is administered). For participants in Cohort B1, persistence of CIS is defined as persistence of CIS at the 12-week disease assessment. This will require a cystoscopy or cytology positive result with biopsy positive for CIS. The date of positive biopsy, cystoscopy, or cytology (whichever positive result is earliest) will be used as the date of persistence of CIS.

**Recurrence of high-grade disease** is defined as re-appearance of high-grade disease (high-grade Ta, T1 or CIS) after ‘start date’ for the following 1) participants without CIS at baseline, 2) after CR for participants with CIS at baseline, or 3) before CR for participants with CIS and concurrent papillary disease at baseline in Cohort A or B1. This will require a cystoscopy or cytology positive result, with biopsy positive for T1, high-grade Ta and/or

CIS. The date of positive biopsy, cystoscopy, or cytology (whichever positive result is earliest) will be used as the date of recurrence of high-grade disease. If recurrence of high-grade disease occurs at the time of progression, progression should be the event. For participants with CIS at randomization, appearance of high-grade disease after a CR is considered recurrence of high-grade disease, while appearance of high-grade disease before a CR is progression.

**Recurrence of low-grade disease** is defined as re-appearance of low-grade disease (low-grade Ta) after ‘start date’. This will require a cystoscopy or cytology positive result, with biopsy positive for low-grade Ta. The date of positive biopsy, cystoscopy, or cytology (whichever positive result is earliest) will be used as the date of recurrence of low-grade disease.

**Progression of disease is defined** as any of the following:

- Lamina propria invasion (e.g., increase from Ta to T1 or CIS to T1)
- Muscle invasive disease (stage  $\geq$  T2)
- Lymph node positive disease (N+)
- Metastatic disease (M1)
- Appearance of high-grade Ta or T1 in participants with CIS only at baseline (Cohort A and Cohort B1) before achieving a CR.

This will require a cystoscopy or cytology positive result with imaging positive and/or biopsy positive for disease progression as described above. The date of positive biopsy, imaging for new lesion, positive cystoscopy, or positive cytology (whichever result is earliest) will be used as the date of progression.

**No Evidence of Disease:** only applies to participants without CIS at baseline (Cohort A and Cohort B2) and is defined as disease that was completely resected prior to ‘start date’ and does not meet the criteria of progression of disease, recurrence of high-grade disease, or recurrence of low-grade disease while on study.

The date of imaging, biopsy, cystoscopy, or cytology (whichever result of the available assessments is earliest) that supports no evidence of disease will be used as the date of no evidence of disease.

